Section D: Purpose and Objectives

This is an exploratory randomized controlled trial study to test feasibility, acceptability, and proof of concept efficacy of Continuous Diffusion of Oxygen (CDO) adjunct therapy for decreasing healing time and reducing tissue dehiscence post breast reconstruction. We will assess the benefit of this novel adjunct therapy on successful closure, tissue oxygenation, scar appearance, and patients centered outcomes including perception of benefit, pain, sleep quality, and quality of life. Since all procedures are bilateral, an internal randomization will be performed based on breast side (left or right). The patients will be given CDO in one breast defined as intervention breast. A 5x5 cm CDO dressing will be placed by the plastic surgeon over the T-inframammary fold after the Dermabond glue and Prineo tape are placed. Then, Silagen (a silicon sheet) will be placed on top of the CDO dressing to secure it in place. The remaining parts of the incision will be covered with Dermabond Glue and Prineo tape. On the contrary, the control breast will be given the standard dressing (Dermabond + Prineo tape). The study device OxyGeni is a Class II medical device which has US Food and Drug Administration (FDA) 510(k) clearance, CE-Mark approval and a Health Canada license for the treatment of wounds.

Outcomes will be assessed on weekly-basis up to 4 weeks. Here are the aims and hypotheses for this study:

Aim1: To assess effectiveness of CDO adjunct therapy in reducing the likelihood of wound complication post-surgical

closure.

H1: CDO adjunct therapy will reduce the likelihood of surgical wound complication including dehiscence and its volume, infection or surgical revision, compare to standard of care dressing.

Aim2: To assess changes in skin perfusion in patients treated with CDO adjunct therapy.

H2: CDO adjunct therapy will improve tissue oxygen saturation in >50% of the patients as compared to baseline (measurements at baseline, 2 weeks, and 4 weeks).

Aim3: To evaluate changes in quality of life, anxiety during dressing change, and psychosocial parameters in patients with a surgical wound treated by CDO adjunct therapy

H3: CDO adjunct therapy will improve subject quality of life, reduce anxiety, and reduce perceived pain and physiological stress response during dressing change compared to the control group.

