There will be an optional follow up visit up to three and six months after the last visit to determine any potential wound complications (e.g., patient unhappiness with the appearance of scar, infection and quality of life etc). During this visit, study coordinator will photograph both incision sites using near-infrared spectroscopy (NIRS, KENT camera) and a digital photo. Practitioner will assess scarring using the SCAR and/or POSAS scale.

Dressing Change: All patients will have their dressing changed weekly (screening/initial visit and visits 1-4), the intervention site will be treated continuously with oxygen from the OxyGeni device. Prior to application of the OxyGeni, research staff will: Select a 5x5cm OxySpur O2 dressing that will cover the wound; Wrap dressing as directed by physician. This may facilitate delivery of oxygen to the incision site or wound bed.

Data collection: - Medical History: Relevant patient medical history (e.g. type of cancer, type of therapy, other comorbidity such as diabetes and stroke, history of surgery, number of prescription and over counter medication, etc) will be collected at baseline via questionnaire or patient electronic health record.

- Social Factors: marital status, years of education, type of work, tobacco history (pack years, current smoker, current use of chewing tobacco, previous smoker, no tobacco history), drug history (current, previous history, no drug history), and alcohol history. These factors will be collected at screening/baseline visit.

Tissue Oxygen Saturation (primary outcome): Tissue oxygenation level will be assessed using Kent Imaging system at baseline and every study visit. The device uses light in the near-infrared spectrum that harmlessly passes through the skin and reflects off the blood supplying the tissue to determine tissue oxygen saturation, a key indicator of tissue health. The NIRS light has two key features that make it useful for measuring the viability of living tissue. Firstly, NIRS light is not absorbed by tissue as much as visible or ultraviolet light. Secondly, NIRS light is mainly absorbed by hemoglobin and water. Most importantly, the wavelength dependent light absorption of hemoglobin differs if it is carrying oxygen from when it is not. This makes NIRS light very useful in detecting oxygenated and deoxygenated blood, which conveys a comprehensive picture of tissue health and the healing capacity of wounds or tissue transplants.

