Visit 5, at minimum 6 months post-op *duration: 50 minutes. This is an optional visit where research staff will take a NIRS image, a Digital Photograph, report adverse events since last visit, and assess patient scar satisfaction using validated questionnaires (PASS and POSAS). Moreover, the plastic surgeon will provide their observation of the scarring using validated questionnaires (SCAR and POSAS). The patient will be seen in the Vascular Clinic (Procedure Room). Female research coordinator will perform all measurements and questionnaires under ethics protocol. Should the patient not be available to attend the clinic in-person, they will have the option to do the questionnaires remotely and upload digital photos of the area via RedCAP. This study visit is added to provide long-term information regarding scarring and effect of study device on long-term healing outcomes.

The research coordinator will make sure at all times that patient does not experience discomfort and all ethical protocols will be followed.

Section G: Sample Size/Data Analysis

G1. Sample Size

How many subjects (or specimens, or charts) will be used in this study? Local: 30 Worldwide: 30

Please indicate why you chose the sample size proposed:

This is an exploratory proof of concept study. The anticipated sample size (n=30) is selected based on resource/budget availability and feasibility to be completed within one year. This sample size is estimated to be sufficient to determine feasibility and proof of concept efficacy of Continuous Diffusion of Oxygen (CDO) adjunct therapy to improve tissue oxygen supply and reduce likelihood of adverse events. Upon initial results and availability of budget, the sample size may be increased to clinically validate the initial observation. In this case, an addendum will be submitted to increase sample size if needed.

G2. Data Analysis

Provide a description of your plan for data analysis. State the types of comparisons you plan (e.g. comparison of means, comparison of proportions, regressions, analysis of variance). Which is the PRIMARY comparison/analysis? How will the analyses proposed relate to the primary purposes of your study?

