The primary outcomes of this study are 1) tissue oxygen saturation level measured using Kent Imaging system and 2) incident of wound related adverse events (e.g., incident wound dehiscence, infection, scar size, and surgical revision). Secondarily outcomes include pain, wound outcomes (e.g. wound size, scar size, wound healing rate, etc assessed using digital photography), area of inflammation (assessed using KENT), and pain (assessed using VAS). Exploratory outcomes include patient quality of life, sleep quality, anxiety, and depression. Baseline between group comparison will be dine using two-sample t-tests, Mann-Whitney U-test, or Chi-square depend on scale/distribution of the variables (i.e., parametric, non-parametric, or binary). We will use general mixed linear model and post-hoc analysis to examine difference between

groups (time, group, and time X group effect) for skin perfusion. We will adjust the results based on baseline incision wound size and duration between baseline and last visit assessment. Subjects with at least one week continue treatment will be included in the analysis. Controlled variables include age, BMI, baseline vascular health. We will use chi-square to estimate whether the number of wound complication incidents is less in the intervention group compared to the control group. Chi-square or repeated ANOVA or Mann-U test depend on scale/distribution of the variable will be used for secondary and exploratory outcomes.

Section H: Potential Risks/Discomforts

H1. Potential Risks/Discomforts

Describe and assess any potential risks/discomforts; (physical, psychological, social, legal, or other) and assess the likelihood and seriousness of such risks:

As any new investigational device, there are some risks, which are anticipated to be minimal in this study. Some of potential risks could be: * Skin related discomfort, erythema (redness), skin rash, dryness and itching. * Skin allergic reaction to dressing adhesive. * Tenderness/minor ache around the dressing application area * Heat sensation and/or perspiration with wearing dressing * Some impairment of mobility due to dressing unit

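### H2 counts StO2 improvement in a bare majority of patients as support for CDO, with no test or margin; if an inert dressing left each patient equally likely to rise or fall, 43% of 30-patient trials would meet it

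*Combined protocol and SAP*

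**What the plan says.** Section D, Aim 2, states H2 as "CDO adjunct therapy will improve tissue oxygen saturation in >50% of the patients as compared to baseline", with "measurements at baseline, 2 weeks, and 4 weeks". It does not say how large a rise counts as improvement, or which visit decides. Section F2 gives a fuller imaging schedule: "Tissue oxygenation level will be assessed using Kent Imaging system at baseline and every study visit".

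Section G2 makes StO2 a primary outcome: "The primary outcomes of this study are 1) tissue oxygen saturation level measured using Kent Imaging system". The analysis given there for skin perfusion is "We will use general mixed linear model and post-hoc analysis to examine difference between" groups, with time, group and time-by-group effects. G2 contains no test of, or interval for, the proportion of patients improved. It does not link the model to H2 and states no significance level. On who is analysed it says: "Subjects with at least one week continue treatment will be included in the analysis".

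Section G1 gives the basis for the sample size: "The anticipated sample size (n=30) is selected based on resource/budget availability and feasibility to be completed within one year". It then adds "This sample size is estimated to be sufficient to determine feasibility and proof of concept efficacy" for CDO in improving oxygen supply and reducing adverse events, and says the sample may be enlarged after initial results if budget allows, through an addendum.

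The more-than-50% figure in H2 is the only numeric criterion that the documents attach to either primary outcome.

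**The concern.** If any rise counts as improvement and StO2 moves only by measurement noise, about half of the patients will improve under a dressing that does nothing. The criterion therefore sits at the no-effect value. Enrolling more patients would not cure this, because under those conditions the chance of exceeding one half stays near one half at any sample size.

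Two design features add to the problem. The baseline image is taken in theatre when the incision is closed (Section F2, baseline visit), so StO2 may change over the following weeks whatever the dressing does. And H2 compares the CDO breast with its own baseline, although each patient has a randomised control breast that would show such a change.

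What is at stake is how primary outcome 1 will be read. A report could state that H2 was supported on 16 of 30 patients while the G2 model shows no difference between breasts, and the plan does not say which takes precedence. That reading would feed the proof-of-concept conclusion, and it could be among the initial results that G1 mentions when it discusses a larger sample.

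**Working it through.** **Inputs**

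- Criterion: more than 50% of patients improved (Section D, H2).
- Number of patients: n = 30 (Section G1). Dropout is not stated, so 24 to 29 evaluable patients is shown as an assumed range.
- Chance p0 that a patient counts as improved under an inert therapy: not in the documents. Base assumption p0 = 0.50 (any rise counts, no drift, no ties, independent patients, one fixed visit), with a range around it.
- Significance level: none stated. Conventional one-sided 5% and 2.5% are used for comparison only.

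The plan gives no power or error figure for H2, and n = 30 rests on resources, so there is no statistical figure to reproduce.

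**1. How often the criterion is met under no effect**

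Let X be the number improved, X ~ Binomial(n, p0). More than half of 30 means X ≥ 16. At p0 = 0.5 the distribution is symmetric, so

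P(X ≥ 16) = [1 − P(X = 15)] / 2 = (1 − 0.1445) / 2 = 0.428.

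For fewer evaluable patients:

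| n | Count needed | P(met), p0 = 0.5 |
|---|---|---|
| 24 | 13 | 0.419 |
| 25 | 13 | 0.500 |
| 26 | 14 | 0.423 |
| 27 | 14 | 0.500 |
| 28 | 15 | 0.425 |
| 29 | 15 | 0.500 |
| 30 | 16 | 0.428 |

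**2. Dependence on p0, at n = 30**

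| p0 | P(X ≥ 16) |
|---|---|
| 0.40 | 0.10 |
| 0.45 | 0.23 |
| 0.50 | 0.43 |
| 0.55 | 0.64 |
| 0.60 | 0.82 |

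Upward drift after surgery raises p0. Downward drift, ties or a minimum required change lower it.

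**3. What 16 of 30 shows**

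The exact (Clopper-Pearson) 95% CI for 16/30 is 34% to 72%, which is compatible with a minority of patients improving.

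**4. What a margin would require, at n = 30**

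| Rule | P(met), p = 0.50 | p = 0.70 | p = 0.75 | p = 0.80 |
|---|---|---|---|---|
| ≥ 20 of 30 | 0.049 | 0.73 | 0.89 | 0.97 |
| ≥ 21 of 30 | 0.021 | 0.59 | 0.80 | 0.94 |

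The exact 95% CI for 21/30 is 50.6% to 85.3%, and for 20/30 it is 47.2% to 82.7%. So 21 is the smallest count whose two-sided 95% lower limit clears 50%.

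**5. Whether that margin suffices when improvement is measured from baseline**

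Suppose drift alone gives p0 = 0.60. An inert device then passes ≥ 20 of 30 with probability 0.29 and ≥ 21 of 30 with probability 0.18. The 4.9% and 2.1% error rates hold only if 50% really is the no-effect value. Side randomisation gives that value for a CDO-minus-control difference in change (ties aside). Nothing in the design gives it for change from baseline.

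**The case against.** The strongest reply is that H2 is a hypothesis listed among others, not a decision rule. It can be read as a statement about the true proportion, in which case 50% is the natural null value and the gap is only that G2 names no matching test. A reader might infer that the trial will be declared positive on 16 of 30, or that enlargement hangs on H2. The documents support neither: no go/no-go rule is written, G1's sufficiency statement covers adverse events as well as oxygen supply, and enlargement is tied to initial results in general, to budget and to an addendum.

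Second, G2 does plan an inferential analysis for this outcome, and a between-breast model is the natural efficacy comparison in this design. That stands, so it would be wrong to say that StO2 has no formal analysis. But the model compares levels between breasts, does not test the proportion in H2, and is not named as the deciding analysis. The two also ask different questions, so differing answers would not in themselves be a contradiction. The fault is that no precedence is stated.

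Third, a reader might take 43% as a fixed property of the plan. It is not. It follows from p0 = 0.50, and the theatre baseline makes that value uncertain in both directions.

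Fourth, this is an exploratory pilot and no significance level is stated for any outcome. That lowers the severity and means there is no single obligatory threshold. It does not rescue a criterion that cannot separate an effect from noise.

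**Conclusion.** The point holds in limited form. The only numeric criterion for a primary outcome is a bare majority improved from baseline, with no minimum change, test or interval, and the analysis section does not take it up. Read as written, 16 of 30 would support H2. Under an inert therapy that leaves each patient equally likely to rise or fall, with no ties and one fixed visit, this occurs 43% of the time at n = 30 and 42% to 50% of the time for 24 to 29 evaluable patients. With drift from the theatre baseline the figure could be 10% (p0 = 0.40), 64% (0.55) or 82% (0.60). The documents do not allow a choice among these.

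The tempting remedy of adding an exact test of change from baseline is not supported either, since it would give formal standing to a comparison whose null value is unknown. The change should be made before the data are read, but given the pilot status it is a correction to how the result is interpreted and not a flaw that stops the trial.

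**What to change.** Adopt one of two changes, in both H2 and G2.

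**(a) Make the figure descriptive.** State that the >50% proportion is descriptive and cannot by itself support proof of concept. State also that the mixed-model group-by-time contrast, CDO versus control breast, decides, and is reported with its confidence interval.

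**(b) Keep a responder criterion, but base it on the control breast.** Define a patient as improved if the change from baseline in StO2 is larger in the CDO breast than in the same patient's control breast, at one named visit. Call H2 supported only if the lower limit of the exact 95% CI for that proportion is above 50%. With 30 patients this means at least 21, and the count must be recomputed for the number analysed. The one-sided error is 2.1%, and power is 59%, 80% and 94% at true proportions of 70%, 75% and 80%.

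Either change takes a sentence or two in each section and needs no new patients. Under (b), control-breast StO2 must be available at baseline and at the named visit. The cost of (b) is a harder criterion: 16 to 20 of 30 would no longer count as support, and power is modest if the true proportion is near 70%. The cost of (a) is giving up a simple patient-level success statement.

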1) Baseline (Surgery Day, Week 0) 2) Visit 1 (Week 1 Post-Op) 3) Visit 2 (Week 2 Post-Op) 4) Visit 3 (Week 3 Post-Op) 5) Visit 4 (Week 4 Post-Op) 6) Visit 5 (minimum of 6 months Post-Op) *optional

Baseline: Subjects will be randomized to internal control. Since all procedures are bilateral, an internal randomization will be performed based on breast side (left or right). The patients will be given CDO in one breast defined as intervention breast. A 5x5 cm CDO dressing will be placed by the plastic surgeon over the T-inframammary fold after the Dermabond glue and Prineo tape are placed. Then, Silagen (a silicon sheet) will be placed on top of the CDO dressing to secure it in place. The remaining parts of the incision will be covered with Dermabond Glue and Prineo tape. On the contrary, the control breast will be given the standard dressing (Dermabond + Prineo tape).

Visits 1-4: All patients will have baseline assessment including visual, dermal, and tissue oxygen saturation level. The status of wound closure and presence of wound complication will be monitored every week. Each subjects will need up to 5 visits including baseline assessment, and weekly assessment up to 4 weeks or full wound healing or surgical revision, whichever comes first. At each visit, patients will be provided standard of care treatment including regular wound dressing change. Table 1 in attachments' section summarizes the key measurement at each study visit. At Visit 4, the CDO therapy will be removed. Subjects will then have the option to return at minimum 6 months later for a final follow-up visit listed below.

Visits 5: Optional follow-up visits. This visit can also be done remotely should the person not be available to attend the clinic.

Inclusion Criteria:

18-85 years of age. Ability to provide informed consent. Presence of a wound due to surgical intervention and closure. Subject or responsible caregiver is willing and able to maintain the required Continuous Diffusion of Oxygen (CDO) system (if assigned to the intervention group) and applicable dressing changes

Exclusion Criteria:

Active Drug/alcohol abuse (or history of drug/alcohol abuse in last 1 month); excessive lymphedema; presence of active infection; subject has a history of or any intercurrent illnesses or conditions that would compromise the safety of the subject according to judgement of a qualified wound specialist.

F2. Procedure

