Please note that subjects will be consented before performing any study related measurements. This study will not bring any direct costs to the subject. The subject's medical insurance will be billed for all standard of care procedures.

Eligible subjects will be internally randomized and will receive the intervention for 4 weeks. Each subjects will receive standard of care for wound treatment. Intervention side will receive adjunct Continuous Diffusion of Oxygen (CDO) therapy using a novel dressing, which facilitates continuous supply of oxygen to the wound inside the wound dressing using a portable device named OxyGeni . We will collect patient demographics (e.g., age, sex, height, weight, race, ethnicity, marital status, level of education, etc), relevant medical history (e.g., comorbidity, type of surgery, number of prescription and over counter medication, etc), and relevant social factors (e.g., marital status, years of education, type of work, tobacco history, etc) at baseline. Primary outcomes include tissue oxygenation (assessed using Kent Imaging system) and incidence of wound complications (e.g. dehiscence, infection, and surgical revision). Primary outcomes will be assessed at baseline and on a weekly basis for up to 4 weeks. Secondary and exploratory outcomes include inflammation (assessed using a KENT camera), pain (assessed visual analog scale). The secondary and exploratory outcomes will be assessed at baseline and week-4. Other optional assessments include quality of life (NIH Global Health PROMIS), depression (Center for Epidemiologic Studies Depression Scale, CES-D), cognitive function MoCA), and psychosocial metrics (e.g. fatigue, anxiety, frailty, sleep, etc). These assessments are optional and will be done upon time availability and patient acceptance. We anticipate that duration of all assessments will not exceed 60 minutes. We will be reviewing the billing records for our

patients to explore costs of both groups. We may visit the patient's home for an appointment that doesn't require the physician present or to fix any issues with the device.

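### H3 compares quality of life with a control group, but all 30 patients receive CDO, so that contrast cannot be estimated; the same holds for anxiety and stress response unless they are measured per breast

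*Combined protocol and SAP*

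**What the plan says.** Section D and F1 describe randomisation of breast side within each patient: "The patients will be given CDO in one breast defined as intervention breast", and the other breast has the standard dressing. F2 confirms this: "Eligible subjects will be internally randomized and will receive the intervention for 4 weeks". G1 plans 30 patients.

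H3 states that CDO will "improve subject quality of life, reduce anxiety, and reduce perceived pain and physiological stress response during dressing change compared to the control group". Aim 3, which H3 serves, is worded differently: "To evaluate changes in quality of life, anxiety during dressing change, and psychosocial parameters in patients". It names no comparator.

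F2 gives PROMIS Global Health as the quality-of-life instrument and lists anxiety among the psychosocial measures. Of these it says: "These assessments are optional and will be done upon time availability and patient acceptance". G2 gives their status: "Exploratory outcomes include patient quality of life, sleep quality, anxiety, and depression". For analysis it says: "Chi-square or repeated ANOVA or Mann-U test depend on scale/distribution of the variable will be used for secondary and exploratory outcomes". It does not say what is compared with what.

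The VAS pain paragraph in F2 has staff record the patient's pain and does not mention side. The only items stated to be collected for each breast are in the scar and satisfaction questionnaires (itch, thickness, discomfort and pain), and these are not tied to dressing change. F1 refers to a Table 1 of measurements by visit, which is an attachment not available here.

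**The concern.** H3 is worded as if there were a separate group of control patients. The inclusion criteria in F1 use similar language, asking for willingness to maintain the "Continuous Diffusion of Oxygen (CDO) system (if assigned to the intervention group"), although no group of patients without CDO is described anywhere. In this trial the control is a breast, not a person. An outcome that exists once per person has no control value.

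What is at stake is how the result is reported. Suppose quality of life or anxiety moves between the surgery-day baseline and follow-up. Under H3's wording the movement would be read as benefit or harm relative to control. The data could not separate a CDO effect from the ordinary post-operative course, and the direction of that course cannot be assumed. Reported as change over time, as in Aim 3, the same numbers would not mislead.

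**Working it through.** The plan's own figure is 30 patients. G1 bases it on resources and feasibility and gives no power, effect size or SD, so there is no calculation to reproduce. The question is whether the H3 contrast can be estimated at all.

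**Inputs.** Patients: 30 (G1). Patients with CDO on one breast: 30 (Section D, F1, F2). Patients without CDO: 30 − 30 = 0. Breasts: 2 × 30 = 60, of which 30 have CDO and 30 are controls.

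**1. One score per patient, one time point.** Model: Yᵢ = a + b·CDOᵢ + error. Since CDOᵢ = 1 for every patient, the CDO column equals the intercept column. The design matrix has rank 1 for 2 parameters. Only a + b can be estimated, not b.

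**2. One score per patient, baseline and follow-up.** Model: Yᵢₜ = a + b·Gᵢ + c·Tₜ + d·GᵢTₜ + error. With Gᵢ = 1 throughout, G duplicates the intercept and G×T duplicates T. The rank is 2 for 4 parameters. The estimable quantities are a + b and c + d. Here c is the post-operative course and d the CDO effect, so the observed change is their sum.

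**3. The patient's score entered for both breasts.** The within-patient difference is Yᵢ − Yᵢ = 0 for every patient, whatever CDO does.

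**4. Patients with CDO on the left against patients with CDO on the right.** Both sets are treated, so this estimates an effect of side and not of CDO.

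**5. One score per breast.** Model: Yᵢⱼ = pᵢ + b·CDOᵢⱼ + error, with 30 patient effects and one CDO effect. The rank is 31 for 31 parameters, so b can be estimated from within-patient differences.

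**Applied to the outcomes in H3:**

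- *Quality of life.* PROMIS is one score per patient, so cases 1 to 3 apply and the contrast cannot be estimated.
- *Anxiety.* Aim 3 ties it to dressing change, so a per-breast rating is conceivable. No instrument or per-breast procedure is described. Cases 1 to 3 apply unless it is measured by breast.
- *Physiological stress response.* Section P lists a Bioharness, but F2 gives no procedure for it. The position is the same as for anxiety.
- *Pain.* Case 5 applies if the VAS is recorded by side. For pain during dressing change a second condition applies: it must be clear whether the control breast has a dressing change at that visit. F1 and the dressing-change paragraph of F2 say patients' dressings are changed weekly. The visit descriptions in F2 detail only the CDO dressing. Section C says the Prineo tape, which is part of the control dressing, stays on for 3 weeks and comes off early if dehiscence occurs.

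**Timing.** F2 places secondary and exploratory outcomes at baseline and week 4. Elsewhere in F2 the VAS is taken at every visit, and the optional questionnaires may be done at any visit. Some patients may therefore have no baseline quality-of-life value, and the change in case 2 could not be computed for them.

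**The case against.** The strongest reply is that the control in H3 can be read as the control breast, that these outcomes are optional and exploratory in a pilot, and that Aim 3 already speaks only of change. Repeated ANOVA, which G2 names, can serve change over time. Much of this stands. It limits the point to H3's comparator wording and to G2's silence on what is compared. The within-patient design itself is not at fault. Reading the control as a breast does not rescue a whole-patient score, however, because the difference is then zero by construction (case 3).

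It is also fair that the anxiety contrast should not be called impossible outright. No anxiety instrument is named, and Table 1 was not available, so a per-breast measurement cannot be excluded.

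A reader might infer more than the documents support in three places:

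- *That all of H3 fails, or that the primary comparisons do.* Pain can be compared by side, and the two primary outcomes can be assessed breast by breast.
- *That some patients go without CDO.* The inclusion wording suggests it, but the design text describes no such group.
- *That a false-positive rate for a before-after test measures the damage.* The documents give no post-operative shift and no completion rate, and G2 names no paired t-test. Any such figure would rest wholly on assumptions, so none is given.

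**Conclusion.** The point holds in limited form. For quality of life, H3's comparison with control cannot be estimated: 0 of 30 patients are untreated and there is one score per patient. More patients or a different test would not change this. For anxiety and physiological stress response the same conclusion depends on there being no per-breast measurement. The available text describes none, but Table 1 could not be checked. Change from baseline can be estimated where both values exist, but it cannot support a claim of benefit over control. Pain is the H3 outcome that this design can control. That requires recording side and, for pain during dressing change, knowing what is done to the control breast at each visit.

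This should be corrected, because it changes what the trial can conclude on a stated hypothesis. It does not touch the two primary outcomes.

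**What to change.** 1. **H3 and G2.** Restate quality of life as descriptive change over time in treated patients, in line with Aim 3. Do the same for anxiety and stress response unless they are measured per breast. Report how many patients have both baseline and follow-up values. Make no CDO-versus-control test and no claim of benefit over control. Treat the other whole-patient exploratory outcomes in G2, sleep and depression, in the same way; H3 does not name them.

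2. **VAS pain in F2.** Record it separately for the left and right breast at each visit. Compare sides with a paired analysis or a mixed model with patient as a random effect. Do not restrict the comparison to visits where both breasts have a dressing change. If the Section C practice holds in the trial, early control-side changes would occur mainly where there is dehiscence, so the restriction could select on a post-randomisation primary outcome. Before pain during dressing change is interpreted by side, reconcile Section C, F1, the dressing-change paragraph and the visit descriptions on whether the control breast has a dressing change at each visit.

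3. **Assessment timing in F2.** Reconcile baseline and week 4 for secondary and exploratory outcomes with VAS at every visit and questionnaires at any visit.

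**Cost.** Wording in Sections D, F2 and G2, and one extra VAS rating per visit if side is not already recorded. The downside is that H3 becomes largely descriptive.
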